Secondary aims: To assess whether resveratrol has antimicrobial and antioxidant activity in adults with bronchiectasis; to determine the optimal dose of resveratrol in terms of anti-inflammatory, antimicrobial, and antioxidant effects, bioavailability, adherence, tolerability and safety in adults with bronchiectasis.

Study design

Single centre, single-arm, pre-post, open-label study in patients with stable bronchiectasis over 12 weeks. The study will incorporate a sub-study, whereby participants will be randomised to receive either 500 mg twice daily, or 1000 mg twice daily

Study centre and recruitment

The study site is Middlemore Hospital, South Auckland. The hospital serves a population of approximately 510,000 people with relatively large Māori (16%) and Pacific (23%) populations. Patients will be identified using a departmental research database of patients with bronchiectasis, and using clinical coding data (ICD-10) for patients attending outpatient clinics and discharged from hospital with a diagnosis of bronchiectasis.

We plan to recruit 40 patients for this study.

Inclusion criteria

- Aged ≥ 18 years
- Able to provide written informed consent
- Able to provide spontaneous sputum sample at visit 2 (week 0)
- High-resolution CT (HRCT) chest scan confirming diagnosis of bronchiectasis within 5 years
- Clinically stable during baseline period, for 4 weeks prior to commencement of treatment (defined as the absence of clinical worsening beyond normal daily variation, with no need for increasing habitual medications or taking antibiotics or prednisone, with stable spirometry)
- History of one or more pulmonary exacerbations requiring antibiotics in the past 12 months.
- Patients with asthma and COPD will be included if the primary diagnosis is bronchiectasis

Exclusion criteria:

- Patient using current oral, intravenous or inhaled antibiotics within 4 weeks prior to commencing study drug
- Patients taking continuous macrolide therapy (≥ 3 months) within 3 months of screening
- Patients taking continuous oral corticosteroids (>6 weeks)
- Bronchiectasis exacerbation or respiratory infection requiring oral or intravenous antibiotic treatment within 4 weeks prior to commencing study treatment
- Use of prescribed or dietary antioxidant supplement within 1 month of screening
- Body mass index <18.5 kg/m²
- Patients with a history of non-compliance with medications
- Patients with significant medical conditions other than bronchiectasis:

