Participants have to be clinically stable for at least 4 weeks with no event-based exacerbations before commencing treatment to ensure clinical stability.

Clinical assessment (visits 1, 2, 3, 4)

This will include documentation of subject characteristics, medications, and measurement of vital signs (pulse, blood pressure, and temperature at every visit. Physical examination (general, cardiovascular, respiratory, abdominal examinations) will be done by an investigator at all study visits.

Simple blood tests (visits 1 and 4)

Blood samples will be taken to measure full blood count (FBC), urea & electrolytes (U&E), liver function tests (LFT) and highly-sensitive C-reactive peptide (hs-CRP) at visits 1 and 4. For female participants of child-bearing potential, a serum β -hCG level (pregnancy test) will be measured at screening (visit 1). A urinary pregnancy test will be done at visit 2 prior to commencement of study medication and again at visit 4.

Sputum analysis

Participants will be asked to provide a baseline spontaneous sputum sample at visit 2. Participants who are productive of only a small volume of sputum or have difficulty expectorating will be asked to provide a baseline sputum sample within one week of visit 2. Samples are also required at visits 3 and 4.

Sputum will be processed using standardised guidelines in keeping with the European Respiratory Society Task Force document regarding sputum induction and processing.^{96,97} Spontaneous sputum specimens (sputum plus saliva) will be obtained at visit 2. If participants are unable to provide a sputum sample at visit 3 or 4, induced sputum samples will be collected (see below); samples will be processed within 2 to 4 hours of collection.

Sputum supernatant for measurement of neutrophil elastase, cytokines, hs-CRP and total antioxidant capacity will be separated and frozen at -70°C for measurement at the completion of the study.

Induction of sputum

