Tolerability will be recorded dichotomously and defined as successful completion of the study. Adherence will be described as percentage of capsules taken calculated from prescribed and returned medication. We will record participation consent probability, recruitment and drop-out events.

End points

Primary end point: Change in sputum neutrophil elastase

Secondary end points:

- Sputum hs-CRP
- Sputum cytokines – GM-CSF, IL-1 β , IL-6, IL-8, TNF- α
- Sputum purulence
- Sputum cathelicidin (LL-37)
- Sputum procalcitonin
- Sputum culture
- Sputum and serum total antioxidant capacity
- Sputum and serum resveratrol levels (and metabolites)
- Pulmonary exacerbation frequency
- Lung function (spirometry: FEV1, FVC)
- Health-related quality of life
 - St George’s Respiratory Questionnaire
 - Bronchiectasis Health Questionnaire
 - Leicester Cough Questionnaire
- Adverse events
- Adherence, tolerability and safety of oral resveratrol supplementation
- Requirement for induction of sputum at Visit 4

Statistical Methods

Analysis plan

The analysis will take place in an intention-to-treat analysis set. Our primary aim is addressed by the hypothesis that the primary outcome (*sputum neutrophil elastase levels*) at visit 4 will decline from high values at visit 2 (baseline), or remain stable from low values at visit 2. Accordingly, the primary analysis will consist in a regression of the change at visit 4 from baseline on the value at baseline, using a suitable parametric model, a flexible smooth model for the baseline value and appropriate adjustments (including adjustments for dosage in interaction with baseline).

The alternative hypothesis then translates as a negative relationship between baseline and difference at visit 4. The model is provisionally identified as lognormal, inferred from the literature, but a data review will be effected to confirm.

Safety data will be reported in detail by arm and stratified by severity and causality, using Common Terminology Criteria for Adverse Events (CTCAE) standard. *Tolerability and adherence* will be regressed on the dosage arm using logistic and linear regression respectively. As this is a signal-finding study, tests will be conducted at a significance level of 10% against two-sided alternatives, with no adjustment for multiplicity.

Sample size

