We have based our sample size on the baseline values from two highly important papers assessing neutrophil elastase levels in bronchiectasis.^{11,101} One study reported median sputum neutrophil elastase levels of 15 µg/ml (IQR 3-23 µg/ml); in the other, levels varied according to stable or exacerbation state, with median of 0.39 µg/ml (IQR 0-23.5 µg/ml).^{11,101} Converting these values to approximate mean and standard deviation using standard techniques yielded estimated lognormal parameters on which we based our simulations. With these parameters and assuming a drop-out rate of 10%, we ran extensive power simulations to establish a detectable decrease at visit 4 from baseline of 40% with 80% power (under any dosage). The detectable difference corresponds to a decrease from 5 to 3 µg/ml between baseline and visit 4. The same sample size enables us to detect a doubling of the efficacy of resveratrol under the 2000 mg vs 1000 mg per day dosage with 80% power, provided the larger dose decreases sputum neutrophil elastase by 67% or more.

Data Monitoring Committee

A data monitoring committee will comprise 3 external members.

- *[name]* (Biostatistician, Ko Awatea, Counties Manukau DHB; Independent) – Chair of committee
- *Assoc. [name]* (Respiratory Physician, Western Health, Melbourne; Co-investigator)
- *[name]* (Respiratory Physician, Department of Respiratory Medicine, Middlemore Hospital; Independent)

References:

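### The primary test reads a negative slope of change on baseline as drug benefit, but regression to the mean makes that slope negative with no drug effect, so its false-positive rate is well above the stated level

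*Protocol*

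**What the plan says.** The design (Protocol, Study design) is a "Single centre, single-arm, pre-post, open-label study in patients with stable bronchiectasis over 12 weeks". Both randomised doses are active.

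Under Statistical Methods, Analysis plan, the hypothesis is that elastase will come down in participants who start high and hold steady in those who start low. From this, "the primary analysis will consist in a regression of the change at visit 4 from baseline on the value at baseline". The form of that regression is left partly open; it is to be fitted "using a suitable parametric model, a flexible smooth model for the baseline value and appropriate adjustments (including adjustments for dosage in interaction with baseline". The decision rule follows: "The alternative hypothesis then translates as a negative relationship between baseline and difference at visit 4". On distribution: "The model is provisionally identified as lognormal, inferred from the literature", subject to a data review. On level: "tests will be conducted at a significance level of 10% against two-sided alternatives, with no adjustment for multiplicity".

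The Sample size section describes a different quantity, an average fall. Simulations were run "to establish a detectable decrease at visit 4 from baseline of 40% with 80% power (under any dosage", illustrated as 5 to 3 µg/ml, with 10% drop-out from 40 participants. The Hypothesis section also speaks of a decrease in elastase levels, not of a slope.

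**The concern.** A value that is high partly by chance at visit 2 tends to be lower at visit 4, and a low one tends to be higher. Regressing the difference on the starting value turns this into a negative slope whether or not the capsule does anything. The pattern that the Analysis plan names as its hypothesis is close to what regression to the mean produces unaided.

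Nothing in the design separates the two. There is no untreated group to supply a no-drug slope. The visit schedule has no elastase measurement before visit 2, so within-patient variation cannot be estimated from repeat pre-treatment samples. The protocol states no null slope other than zero.

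This is the primary analysis of a study meant to inform a large placebo-controlled trial. A significant result could not be told apart from ordinary biological and assay variation.

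**Working it through.** **Inputs from the protocol.** 40 recruited and 10% drop-out give 36 completers; two-sided 10%, so 5% in the negative direction; a 40% fall, ln(0.6) = −0.511; provisional lognormal model; published median 15 (IQR 3–23) and median 0.39 (IQR 0–23.5) µg/ml.

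**Assumed.** The visit 2 to visit 4 correlation rho is not given, so it is varied.

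**Log SD.** The protocol does not print its converted values. With mean = (q1 + median + q3)/3, SD = (q3 − q1)/1.35 and log SD = √ln(1 + (SD/mean)²):
- First study: mean 13.7, SD 14.8, log SD 0.88.
- Second study: mean 8.0, SD 17.4, log SD 1.32.
- Pooled: √((0.88² + 1.32²)/2) ≈ 1.12.
- Directly from the first IQR: ln(23/3)/1.349 = 1.51.

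**The plan's own 80%.** A test of mean log change with n = 36 has 80% power when the SD of the log change is about 1.21. Since that SD equals log SD × √(2(1 − rho)), rho = 1 − 1.21²/(2 × log SD²). This gives rho of about 0.06, 0.42, 0.58 and 0.68 for log SD 0.88, 1.12, 1.32 and 1.51. The stated 80% can therefore be matched but not verified: neither rho nor the simulated test is stated.

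**Slope with no drug effect.** Let X and Y be log elastase at visits 2 and 4, with equal SD. Then

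slope = cov(Y − X, X)/var(X) = rho − 1, with SE = √((1 − rho²)/(n − 2)).

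For rho 0.8: slope −0.20, SE = √(0.36/34) = 0.103, expected t about −1.94, already beyond the critical value of −1.69. The rejection rates below are from 20,000 simulated trials per setting with an inert capsule; the raw-scale ranges span log SD 0.88 to 1.51.

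| rho | expected slope | SE | significant negative slope, log scale | same, raw scale |
|---|---|---|---|---|
| 0.5 | −0.50 | 0.149 | 94% | 74–80% |
| 0.67 | −0.33 | 0.127 | 81% | 66–69% |
| 0.8 | −0.20 | 0.103 | 60% | 59–60% |
| 0.9 | −0.10 | 0.075 | 37% | 49–52% |
| 0.95 | −0.05 | 0.054 | 24% | 42–48% |

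The log-scale rates do not depend on the log SD. They pass 50% when rho is below about 0.85 (0.86 with all 40 participants). At rho 0.98 the rate is still about 15%.

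**Planned adjustments.** With a dose-by-baseline term the log-scale rates are 96%, 74%, 57% and 35% at rho 0.4, 0.7, 0.8 and 0.9. A three-df spline F-test, nominal 10% and without direction, rejects in 92%, 64%, 46% and 28%. Neither removes the problem.

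**With a true uniform 40% fall.** If log change is regressed on log baseline, only the intercept moves: rejection is 97% with or without the fall at rho 0.4. On the raw scale the slope steepens, and rejection rises from 74–80% to 89–97% at rho 0.5 and from 49–52% to 89–98% at rho 0.9.

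**Mean log change tested against zero.** Type I error is about 10% at every rho. Power for a 40% fall, for log SD 1.51 to 0.88, is 64–96% at rho 0.5, 79–99% at 0.67 and at least 93% at 0.8.

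**The case against.** Four points can be made for the plan.

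*The test does respond to the effect it was sized for.* A reader might infer that the slope test is blind to the 40% fall. That holds only if log change is regressed on log baseline. The Analysis plan does not fix the scale; its wording and the 5 to 3 µg/ml illustration also fit a raw difference, on which a uniform proportional fall is itself a negative slope. This stands. On the raw scale the fault is false positives, not insensitivity.

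*The size depends on an unstated correlation.* A reader might infer that an inert capsule would usually be declared effective. The documents do not support that without conditions: it needs rho below about 0.85 for the simple log-scale slope, and lower for a spline test. What is certain is that the expected slope is negative for any rho below 1, not that a given trial will reject. If the stated 80% power refers to mean change, the matching rho values (0.06 to 0.68) lie well inside the region above 50%, but the protocol does not say which test was simulated.

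*It is a pilot.* The signal-finding label justifies a 10% level. It does not justify rates of 24% to 94% in one direction. That the next step is a placebo-controlled trial limits the harm without removing it.

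*The dose comparison is randomised.* This stands: both arms share the same expected regression to the mean, so that contrast is sound in this respect. It serves a secondary aim and does not rescue the primary test.

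**Conclusion.** The point holds. The decision rule is explicit, so an analysis plan that follows the protocol inherits it. A zero slope is not the no-effect null in this design, and no comparator or replicate baseline supplies the right one.

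With 36 completers the false-positive rate in the benefit direction is about 94% to 24% on the log scale, and about 74–80% to 42–48% on the raw scale, as rho runs from 0.5 to 0.95, against a nominal 5%. These figures assume bivariate lognormal values with the same distribution at both visits.

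Two further inferences go beyond the documents: that the result would be a false positive for any plausible correlation, and that the randomised dose contrast is also compromised.

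**What to change.** In Analysis plan, delete the slope-based alternative. Make the primary effect the geometric mean ratio of elastase at visit 4 to visit 2, pooled over doses, tested as mean log change against a ratio of 1 at two-sided 10% and reported with its 90% confidence interval.

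Set in advance a rule for zero or below-detection values, since one source study has a lower quartile of 0: for example a fixed substitution at the assay limit, or a censored lognormal model.

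In Sample size, restate the power for this test with the log SD and rho used. At log SD 1.51 and rho 0.5 it is about 64%, short of 80%.

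Keep baseline dependence as exploratory, by a method free of the coupling: change against the mean of the two visits, or a comparison of the visit 2 and visit 4 variances.

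State that the result remains an uncontrolled pre-post change. Entry is not selected on elastase, so the mean change is not driven by regression to the mean as the slope is. Time trend remains, and so does the difference between spontaneous sputum at visit 2 and possibly induced sputum later.

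Optionally, use the visit 3 samples already planned ("Samples are also required at visits 3 and 4") in a repeated-measures model; the repair does not depend on it.

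The cost is wording in the protocol and any analysis plan, with no extra participants, visits or samples.

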C O U N T I E S
M A N U K A U
H E A L T H

Division of Medicine
Middlemore Hospital
Counties Manukau Health
[name]
[name]

Title: **Anti-inflammatory and antioxidant effects of oral resveratrol in bronchiectasis**

Study funder: Counties Manukau Health

Principal Investigator: [name]
Respiratory Research Fellow
Respiratory Medicine
Middlemore Hospital
Otahuhu
Auckland
[contact]

Ethics Reference Number: *To be confirmed*

Australian New Zealand Clinical Trials Registry (ACTRN) number: *To be confirmed*

Study product name: Transmax (Resveratrol 500 mg + Polydatin 5 mg + Piperine 5 mg)

Protocol version/date: Original (v1) 9th March, 2020

PROTOCOL SYNOPSIS

Anti-inflammatory & antioxidant effects of resveratrol in bronchiectasis: A pilot study

Rationale for research

- Bronchiectasis is a chronic, debilitating disease characterised by recurrent and chronic respiratory infection requiring antibiotics and intense neutrophilic inflammation.¹ Antibiotic resistance is increasing globally, and novel treatments are needed urgently.²
- The naturally-occurring antioxidant supplement resveratrol exhibits antibacterial activity against *H. influenzae*³⁻⁵ and suppresses markers of neutrophilic inflammation.⁶⁻⁸ Antioxidant supplementation has been shown to reduce exacerbations in cystic fibrosis.⁹
- We ultimately plan to undertake a large, randomised, placebo-controlled trial of resveratrol supplementation in bronchiectasis. However, several feasibility issues need to be evaluated before undertaking such a study. These include determining effects of resveratrol treatment on airway inflammation and antioxidant status in patients with bronchiectasis. We will also evaluate tolerability and safety of resveratrol in bronchiectasis.
- Potential benefits of resveratrol treatment for bronchiectasis include fewer exacerbations, improved quality of life and reduced healthcare utilisation.

Aims

Primary aim: To assess whether oral resveratrol has anti-inflammatory effects in adults with bronchiectasis.

Secondary aims: To assess whether oral resveratrol has antimicrobial and antioxidant activity. To determine the optimal dose of resveratrol (1000 mg daily vs 2000 mg daily) in terms of anti-inflammatory, antimicrobial, and antioxidant effects, bioavailability, adherence, tolerability, and safety.

Research design and methods:

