 - A significant disease is one that would, in the opinion of the investigator, put the participant at risk through participation in the study, or a disease which may influence the results of the study, or the participant's ability to participate in the study.
- Patients with cystic fibrosis
- Patients with primary ciliary dyskinesia
- Patients with hypogammaglobulinaemia

- Patients with allergic bronchopulmonary aspergillosis (defined as the presence of asthma, total serum IgE > 1000 IU/ml, with detectable specific IgE to Aspergillus or positive Aspergillus skin test)
- Patients taking immunosuppressive agents (e.g. azathioprine, methotrexate, cyclophosphamide)
- Patients with other primary or acquired immunodeficiency
- Patients with evidence of active or suspected cancer and patients having undergone cancer treatment including resection, radiation therapy or chemotherapy within the last 2 years (patients with basal cell carcinoma and squamous cell carcinoma are allowed)
- Pregnant or lactating women
- Participation in a separate clinical or device trial within 4 weeks of screening
- Allergy to any of the components of Transmax

Reasons for discontinuation of study medication

- Participant request to discontinue treatment
- Adverse event that contraindicated further dosing, in the opinion of the investigator
- Risk to subject, as judged by the investigator
- Pregnancy
- Discontinuation of the study at the request of the Data Monitoring Committee or regulatory agency, institutional review board or independent ethics committee

Participants who prematurely discontinue treatment should continue in the study until the final visit, if possible. It is highly recommended that all study procedures, including any scheduled visits, are continued until the final visit, if possible.

Withdrawal of participants from the study

- Participant request to withdraw from study
- Lost to follow-up
- Investigators deem that participants are at significant risk of harm from study medication or procedures
- The Data Monitoring Committee requests patient withdrawal due to major safety concerns

Criteria for termination of the study

- Investigators deem that participants are at significant risk of harm from study medication or procedures
- Investigators reserve the right to terminate the study if adequate resources or funding are no longer available to continue the study

Study medication

Investigational products

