An adverse event (AE) is defined as any untoward medical occurrence, including an exacerbation of an existing condition in a trial participant receiving a pharmaceutical product. The event does not necessarily have to have a causal relationship with this treatment.

A serious adverse event is defined as any AE which results in death, is immediately life threatening, results in persistent or significant disability, requires or prolongs participant hospitalisation, is a congenital anomaly or birth defect, or is an important medical event that may jeopardise the patient or require intervention to prevent one of the above outcomes.

It is the responsibility of the investigator to record and report all AEs (both serious and non-serious) occurring during the course of the clinical trial (from signing the informed consent form through to the end of the trial). It will be derived by spontaneous, unsolicited reports of patient, by observation and by routine open questionings such as "Has there been any change in your health since I last saw you".

All adverse events will be fully documented on the worksheet with the onset, intensity, seriousness, outcome and action taken, including change in dosage of study drug.

All serious adverse events and unexpected serious adverse reactions (SUSARs) will be reported to the study Data Monitoring Committee. The Health and Disability Ethics Committee (HDEC) do not require notification of SAEs and SUSARs but *urgent safety measures* (to protect participants from a serious, immediate hazard to their health and safety) will be notified to the HDEC within 7 days.

Clinical trial participants alert card

Participants will also be issued with a clinical trial participant's alert card containing information of the study and contact phone numbers of the study staff, to carry throughout the duration of the study.

Study Procedures

There will be 4 visits (screening [visit 1]; treatment commencement [visit 2]; 4 weeks [visit 3]; and 12 weeks [visit 4]).

There will be a 2-4 week baseline period between screening (visit 1) and commencing treatment (visit 2). At visit 2, patients will be randomised to receive either 500 mg twice daily, or 1000 mg twice daily. Participants will be randomized in a ratio of 1:1, with 20 participants in each group of the sub-study. Randomisation will be performed with the use of a computer-generated sequence with random block sizes of 2 and 4.

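### The protocol describes all three data monitoring committee members as external, but its own list names one as a co-investigator and places another in the study site's respiratory department

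*Protocol*

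**What the plan says.** The Data Monitoring Committee section opens with the statement "A data monitoring committee will comprise 3 external members" and then lists them with affiliation and status:

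- the chair: "Biostatistician, Ko Awatea, Counties Manukau DHB; Independent";
- a second member: "Respiratory Physician, Western Health, Melbourne; Co-investigator";
- a third member: "Respiratory Physician, Department of Respiratory Medicine, Middlemore Hospital; Independent".

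On the site, Study centre and recruitment says "The study site is Middlemore Hospital, South Auckland", and the design is single-centre. The title page gives "Study funder: Counties Manukau Health" and places the principal investigator in Respiratory Medicine at Middlemore Hospital.

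On the committee's duties, the Adverse events section says "All serious adverse events and unexpected serious adverse reactions (SUSARs) will be reported to the study Data Monitoring Committee". The list of grounds for withdrawing participants includes "The Data Monitoring Committee requests patient withdrawal due to major safety concerns". A committee request to discontinue the study appears among the reasons for discontinuation of study medication.

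**The concern.** An investigator on a study is not external to it, so the opening sentence of the section conflicts with the list beneath it. The third member's affiliation adds to the conflict, because that department is at the only site and is the service in which the principal investigator works.

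What is at stake is safety oversight. The protocol says the ethics committee does not need to be told of serious adverse events or SUSARs and will be notified only of urgent safety measures. That leaves the monitoring committee as the one body named as receiving individual serious events. Most other safety judgements in the protocol, such as stopping study medication for an adverse event or ending the study because of harm, are left to the investigators. Treatment is open-label with no untreated arm, and safety and tolerability in this population is one of the study questions. A co-investigator who is a full member of the committee is on both sides of a check that the protocol presents as external. An ethics committee relying on the description would be misinformed.

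**Working it through.** No power or error-rate calculation applies. The check is a count from the protocol's own list, under each plausible meaning of *external*.

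**Inputs**

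- Stated number of external members: 3 (Data Monitoring Committee).
- Members' affiliations and status labels: same section.
- Single site, Middlemore Hospital: Study centre and recruitment.
- Funder and the principal investigator's department: title page.
- Chair's employer taken to be the host and funder: an inference. The title page carries the Counties Manukau Health name for both the hospital and the funder, and the Background section on the scope of the trial refers to local prevalence within Counties Manukau DHB. The protocol never says outright that the two names are one organisation.

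**Classification**

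| Member | Outside the study team (by label) | Outside the host institution |
|---|---|---|
| Chair, biostatistician at the health board | Yes | No, if the inference holds |
| Respiratory physician, Melbourne | No, co-investigator | Yes |
| Respiratory physician, Middlemore | Yes | No |

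**Counts against the stated 3**

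- *External* as outside the study team: 1 + 0 + 1 = 2 of 3.
- *External* as outside the institution: 0 + 1 + 0 = 1 of 3. If the health board were in fact a separate organisation, the chair would also count, giving 1 + 1 + 0 = 2 of 3.

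The stated figure of 3 is not reproduced on any reading. The first count fails because of the co-investigator and the second because of the Middlemore physician, so the conclusion does not depend on the inference about the chair.

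**Internal evidence that the difference was recognised**

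The list labels the chair and the Middlemore physician independent and withholds that label from the co-investigator. The distinction was drawn member by member, yet the opening sentence covers all three.

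**The case against.** The strongest case on the other side is that this is a wording slip in a small pilot. The co-investigator's status is disclosed openly. By the protocol's own labels, two of the three members, including the chair, are independent. The study has 40 participants, lasts 12 weeks and uses a commercially available supplement that the protocol describes as well tolerated. Nothing in it requires a committee drawn wholly from outside the institution.

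Much of this stands, and it rules out several stronger readings:

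- **That the committee has no independence.** A shared employer conflicts with *external*, but nothing shows that either member labelled independent has a role in the trial.
- **That no member is properly external.** A count of 0 of 3 results only if each member must be outside both the study team and the institution. The protocol sets no such double standard.
- **That this is the only safety check separate from the investigators.** The protocol also allows for discontinuation at the request of a regulator, review board or ethics committee, and urgent safety measures go to the ethics committee within 7 days. The supportable claim is narrower: the committee is the only named recipient of individual serious events.
- **That a co-investigator votes on continuing their own study.** No voting, quorum or recusal rule is given. The document shows listed membership without any stated restriction.
- **That the membership could bias the primary result.** The committee's described functions are safety functions. Treatment is open-label, and no interim efficacy analysis or efficacy stopping rule is described.

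The objection does not remove the contradiction. Disclosing the co-investigator's status a few lines later does not make the opening sentence true. The small size of the study limits the consequence, but the correction is correspondingly cheap.

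**Conclusion.** The point holds as a factual error about committee membership, with a limited but real consequence for safety oversight. At most 2 of the 3 members are external to the study team and 1 of 3 is external to the institution, or 2 of 3 if the chair's health board is distinct from the host. The first count takes the protocol's independent labels at face value.

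The firm part is the co-investigator, who cannot be external to the study. The Middlemore physician is firmly internal to the site, but not shown to be part of the trial team. The chair's tie to host and funder is probable, not stated.

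This is not something a statistical analysis plan would settle, because the protocol makes a positive statement that its own list disproves. It should be corrected, but it does not put the analysis in doubt.

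**What to change.** Two changes to the Data Monitoring Committee section:

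1. Replace the co-investigator with someone who is not an investigator on the study. Alternatively, keep the co-investigator as a non-voting attendee who takes no part in the committee's safety recommendations, and say so.
2. Replace the description of three external members with a true statement of each member's relation to the study team, the site and the funder. The two members labelled independent may stay, provided their institutional affiliation is disclosed in that statement.

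The cost is a short search for one replacement or, under the alternative, a committee with two deciding members, plus a few lines of protocol text. The choice of design, analysis and sample size is untouched.
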